The CDC guidelines for PrEP indicate that HIV testing is required before PrEP initiation to confirm the person does not have HIV. When oral PrEP is used, it is recommended to repeat HIV testing every 3 months before refilling or reissuing the PrEP prescription. When CAB LA PrEP is used, HIV testing is recommended every 2 months, at the time the injection is administered.⁷ HIV testing for PrEP should consist of a laboratory antigen/antibody test or a point-of-care fingerstick antigen/antibody test; rapid tests using oral fluids lack the sensitivity to detect recent infection.⁷

PrEP clinical care represents an opportunity to provide reproductive & sexual health-related services, such as STI screening. The CDC guidelines for PrEP recommends regular screening for syphilis, gonorrhea and chlamydia.⁷ A systematic review of 91 PrEP programs implementing STI testing services in 32 countries found that only 70% of PrEP programs conducted STI screening before PrEP start, and 70% screened for STI every 3 months. However, in high-income countries, screening was high for gonorrhea (92%), chlamydia (92%) and syphilis (87%), but low for hepatitis A (18%) and hepatitis C (43%).¹² In the US, a survey study found that among 809 current or former PrEP users, 91% reported receiving HIV testing at every PrEP care visit. As for STI screening, a blood sample, urine/urethral swab or a rectal swab was collected at every PrEP care visit in 67%, 57% and 36% of participants, respectively.¹³

It is important to understand patterns of PrEP use among people with incident HIV diagnosis to

improve public health and clinical practice. This study will also provide crucial real-world evidence on incident HIV diagnoses on PrEP, PrEP coverage, HIV testing and STI screening in individuals on either oral or LA PrEP.

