7. RESEARCH METHODS

7.1. Study Design

A cohort study using secondary data from the OPERA[®] (Observational Pharmacology Epidemiology Research & Analysis) cohort will be used to answer the study objectives. OPERA is a multi-site observational database collecting data prospectively from the complete electronic health records (EHR) from clinical care throughout the US.

[figure not shown]
Analyses to meet the study objectives will be conducted twice during the study period. Analysis #1 will include data from 01JAN2021-31DEC2023 (Obj. 1-1a) and from 21DEC2021 to 30JUN2024 (Obj 2-6). Analysis #2 will be a repeat of Analysis #1 with data from 1JAN2021-31DEC2024 (Obj. 1-1a) and from 21DEC2021 to 30JUN2025 (Obj 2-6). A

summary of the study design is provided in Table 1 (exposure groups, index date, censoring criteria, endpoints) and in Figure 1 (timeline).

Table 1. Summary of study design

		Analysis #1	Analysis #2
Obj 1 Among all people without HIV in OPERA	Exposure groups	Calendar years	Calendar years
	Index date	NA	NA
	Censoring criteria	NA	NA
	Endpoints	HIV diagnosis	HIV diagnosis
Obj 1a Among people with a new HIV diagnosis	Exposure groups	PrEP use (never, use within ≤12 months before diagnosis, use >12 months before diagnosis)	PrEP use (never, use within ≤12 months before diagnosis, use >12 months before diagnosis)
	Index date	Date of HIV diagnosis	Date of HIV diagnosis
	Censoring criteria	NA	NA
	Endpoints	NA	NA
Obj 2-5 Among PrEP users	Exposure groups	Oral PrEP, CAB LA PrEP	Oral PrEP, CAB LA PrEP
	Index date	Start of first PrEP regimen during the study period	Start of first PrEP regimen during the study period
	Censoring criteria	Death, loss to follow-up (12 months after last clinical contact), study end (30JUN2024), 12 months after index date	Death, loss to follow-up (12 months after last clinical contact), study end (30JUN2025), 12 months after index date
	Endpoints	HIV diagnosis, PrEP coverage, HIV testing, STI screening, STI diagnoses	HIV diagnosis, PrEP coverage, HIV testing, STI screening, STI diagnoses
Obj 6 Among people who could benefit from PrEP	Exposure groups	NA	NA
	Index date	First OPERA visit with indication for PrEP during study period	First OPERA visit with indication for PrEP during study period
	Censoring criteria	Death, loss to follow-up, study end (30JUN2024), 12 months after index date, PrEP initiation	Death, loss to follow-up, study end (30JUN2025), 12 months after index date, PrEP initiation

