- Coverage by LA PrEP will be determined based on the duration of medication from injection date forward. The number of days of coverage per injection were derived from the CAB LA PrEP USPI label.¹⁴
 - 1st injection: coverage = 37 days (30 days of coverage + 7-day injection window)
 - Subsequent injections: coverage = 67 days (60 days of coverage + 7-day injection window)
 - Each calendar day will only be counted once, even if there is an overlap between coverage from the prior injection and date of the next injection.

$$\% \text{ coverage} = \frac{\sum \min(\text{coverage, days between injections})}{\text{Number of FU days}} \times 100\%$$

HIV testing & STI screening

- HIV testing
 - Assessed within 14 days before PrEP start and over the first 12 months after PrEP start
 - Frequency and rate (per 100 person years) of HIV tests over 12-month period
 - Type of HIV tests (RNA [quantitative, qualitative], antigen/antibody, rapid screen)
 - Timing of HIV tests as recommended by PrEP clinical guidelines⁷
 - Oral PrEP: on-schedule testing defined as receiving an HIV test ≤14 days before/at start, and 3 months (76-104 days) after each test
 - LA PrEP: on-schedule testing defined as receiving an HIV test ≤14 days before/at first injection, and ±14 days of each subsequent injection
 - HIV testing practices (type, frequency) by type of healthcare provider (MD or DO, physician associate, nurse practitioner, other/unknown)
 - HIV testing practices (type, frequency) by clinic type (healthcare center, wellness center, other)
- STI screening
 - Assessed within 14 days before PrEP start and over the first 12 months after PrEP start
 - Frequency and rate (per 100 person years) of STI testing events (testing for multiple STIs on the same day will count as 1 testing event)
 - Type of other STI tests
 - Syphilis
 - Gonorrhea
 - Chlamydia
 - Chancroid
 - Lymphogranuloma venereum

- Mycoplasma genitalium
- Hepatitis B virus (HBV)
- Hepatitis C virus (HCV)
- HSV-2
- Trichomoniasis
- HPV and/or genital warts
- Timing of STI tests as recommended by PrEP clinical guidelines⁷
 - Testing 3 months (76-104 days) after last test
 - Testing 6 months (168-196 days) after last test
 - Testing 12 months (351-379 days) after last test
- STI screening practices (type, frequency) by type of healthcare provider (MD or DO, physician associate, nurse practitioner, other/unknown)
- STI screening practices (type, frequency) by clinic type (healthcare center, wellness center, other)

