HIV test within 14 days before/on day of PrEP type start, n (%)		
Test type		
RNA only, n (%)		
Quantitative RNA test, n (%)		
Qualitative RNA test, n (%)		
Ag/Ab only, n (%)		
Rapid test only, n (%)		
Both RNA and Ag/Ab, n (%)		
Quantitative RNA test, n (%)		
Qualitative RNA test, n (%)		
Both RNA and rapid test, n (%)		
RNA, Ab/Ag and rapid tests, n (%)		
Days from test to PrEP type start, median (IQR)		
Any HIV test within 12 months after PrEP type start, n (%)		
Total number of testing events ^b , N		
Test type		
RNA only, n (%)		
Quantitative RNA test, n (%)		
Qualitative RNA test, n (%)		
Ag/Ab only, n (%)		
Both RNA and Ag/Ab, n (%)		
Quantitative RNA test, n (%)		
Qualitative RNA test, n (%)		
Number of HIV testing events ^b per person, median (IQR)		
Average testing interval per person (#testing events /weeks on PrEP type), median (IQR)		
Testing on schedule (oral: every 3 months (76-104 days); CAB LA: ±14 days of each injection), n (%)		

^a Tests are only counted for the PrEP type used at the time of diagnosis

^b Multiple HIV tests on the same day count as one testing event

Table 15. Frequency and type of HIV tests among oral PrEP users, by healthcare provider type ^a

	MD or DO	Physician Assistant	Nurse Practitioner	Other/unknown
Total number of HIV testing events ^b ordered				
Test type				
RNA only, n (%)				
Quantitative RNA test, n (%)				
Qualitative RNA test, n (%)				
Ag/Ab only, n (%)				
Rapid test only, n (%)				
Both RNA and Ag/Ab, n (%)				
Quantitative RNA test, n (%)				
Qualitative RNA test, n (%)				
Both RNA and rapid test, n (%)				
RNA, Ab/Ag and rapid tests, n (%)				
Testing on schedule (≤14 days before/at start or 3 months (76-104 days) after the last test, as applicable), n (%)				

^a Assessed at the test-level

^b Multiple HIV tests on the same day count as one testing event

Table 16. Frequency and type of HIV tests among CAB LA PrEP users, by healthcare provider type^a

	MD or DO	Physician Associate	Nurse Practitioner	Other/unknown
Total number of HIV testing events ^b ordered				
Test type				
RNA only, n (%)				
Quantitative RNA test, n (%)				
Qualitative RNA test, n (%)				
Ag/Ab only, n (%)				
Rapid test only, n (%)				
Both RNA and Ag/Ab, n (%)				
Quantitative RNA test, n (%)				
Qualitative RNA test, n (%)				
Both RNA and rapid test, n (%)				
RNA, Ab/Ag and rapid tests, n (%)				
Testing on schedule (≤14 days before/at first injection or ±14 days of each subsequent injection, as applicable), n (%)				

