Human papilloma virus/genital warts, n (%)		
HBV, n (%)		
HCV, n (%)		
Average screening interval per person (# screening events/weeks on PrEP type), median (IQR)		
Testing every 3 months (76-104 days) ^c , n (%)		
Testing every 6 months (168-196 days) ^d , n (%)		
Testing every 12 months (351-379 days) ^e , n (%)		

^a Tests are only counted for the PrEP type used at the time of diagnosis

^b Multiple STI tests on the same day count as one screening event

^c Recommended gonorrhea, chlamydia and syphilis screening interval for MSM and transgender women who have sex with men

Protocol for Non-Interventional Studies PASS Studies and Non-PASS Studies (4.0) March 2024

Template Doc ID: TMF-15706807

Parent Doc ID: VQD-SOP-066694

^d Recommended gonorrhea and syphilis screening interval for heterosexual women and men

^e Recommended chlamydia screening interval for heterosexual women and men

Table 21. Frequency and type of STI screening among **oral** PrEP users, by healthcare provider type^a

	MD or DO	Physician Associate	Nurse Practitioner	Other/unknown
Total number of STI screening events ^b ordered				
STI tested, n (%)				
Syphilis				
Gonorrhea				
Chlamydia				
Chancroid				
Lymphogranuloma venereum				
Mycoplasma genitalium				
Herpes Simplex-2				
Trichomoniasis				
Human papilloma virus/genital warts				
HBV				
HCV				
Testing 3 months (76-104 days) after last test ^c , n (%)				
Testing 6 months (168-196 days) after last test ^d , n (%)				
Testing 12 months (351-379 days) after last test ^d , n (%)				

^a Assessed at the test-level

^b Multiple STI tests on the same day count as one screening event

^c Recommended gonorrhea, chlamydia and syphilis screening interval for MSM and transgender women who have sex with men

^d Recommended gonorrhea and syphilis screening interval for heterosexual women and men

^e Recommended chlamydia screening interval for heterosexual women and men

Table 22. Frequency and type of STI screening among CAB LA PrEP users, by healthcare provider type^a

	MD or DO	Physician Associate	Nurse Practitioner	Other/unknown
Total number of STI screening events ^b ordered				
STI tested, n (%)				
Syphilis				
Gonorrhea				
Chlamydia				
Chancroid				
Lymphogranuloma venereum				
Mycoplasma genitalium				
Herpes Simplex-2				
Trichomoniasis				
Human papilloma virus/genital warts				
HBV				
HCV				
Testing 3 months (76-104 days) after last test ^c , n (%)				
Testing 6 months (168-196 days) after last test ^d , n (%)				

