	Oral PrEP N=	CAB LA PrEP N=
HIV testing on schedule (oral: every 3 months (76-104 days); CAB LA: ±14 days of each injection), n (%)		
STI screening every 3 months (76-104 days) ^c , n (%)		
STI screening every 6 months (168-196 days) ^d , n (%)		
STI screening every 12 months (351-379 days) ^e , n (%)		
HIV testing NOT on schedule (oral: every 3 months (76-104 days); CAB LA: ±14 days of each injection), n (%)		
STI screening every 3 months (76-104 days) ^c , n (%)		
STI screening every 6 months (168-196 days) ^d , n (%)		
STI screening every 12 months (351-379 days) ^e , n (%)		

\$(vault:document_date__v)

Protocol for Non-Interventional Studies PASS Studies and Non-PASS Studies (4.0) March 2024

Template Doc ID: TMF-15706807

Parent Doc ID: VQD-SOP-066694

Table 26. STI diagnoses among PrEP users^a

	Oral PrEP N=	CAB LA PrEP N=
STI diagnosis within 14 days before/on day of PrEP type start, n (%)		
Any, n (%)		
Syphilis, n (%)		
Gonorrhea, n (%)		
Chlamydia, n (%)		
Chancroid, n (%)		
Lymphogranuloma venereum, n (%)		
Mycoplasma genitalium, n (%)		
Herpes Simplex-2, n (%)		
Trichomoniasis, n (%)		
Human papilloma virus/genital warts, n (%)		
HBV, n (%)		
HCV, n (%)		
STI diagnosis within 12 months after PrEP type start, n (%)		
Any, n (%)		
Syphilis, n (%)		
Gonorrhea, n (%)		
Chlamydia, n (%)		
Chancroid, n (%)		
Lymphogranuloma venereum, n (%)		
Mycoplasma genitalium, n (%)		
Herpes Simplex-2, n (%)		
Trichomoniasis, n (%)		
Human papilloma virus/genital warts, n (%)		
HBV, n (%)		
HCV, n (%)		

^a Tests are only counted for the PrEP type used at the time of diagnosis

Table 27. Incidence rate of STI diagnoses within 12 months of index among PrEP users^a

	Oral PrEP N=	CAB LA PrEP N=
Total # STI diagnoses within 12 months of index, n		
Person-years of follow-up		
IR per 100 py (95% CI)		

Table 28. Identification of the people who could benefit from PrEP population

	Included N (%)	Excluded N (%)
All individuals in OPERA		
≥1 clinical encounter between 21DEC2021 and 30JUN2023		
≥18 years old at first clinical encounter in study period		
Any indication for PrEP ^a		
No PrEP use between 21DEC2021 and 30JUN2023		

^a Bacterial STI in past 12 months (gonorrhea, syphilis, chlamydia), alcohol use disorder, illicit non-injection drug use, injection drug use. Black woman, transgender woman, men who have sex with men, aged 18-24 years, any history of PrEP use

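### Four table-shell rows labelled as an average testing or screening interval are defined as events per week, and in the two tables for people not on PrEP the denominator is not usable

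*Protocol*

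**What the plan says.** Annex 1 of the Protocol gives the HIV testing row of Table 14 (PrEP users, oral and CAB LA columns side by side) as "Average testing interval per person (#testing events /weeks on PrEP type), median (IQR"). The STI row of Table 20 has the same form: "Average screening interval per person (# screening events/weeks on PrEP type), median (IQR"). Both rows reappear unchanged in Table 33 (HIV testing) and Table 38 (STI screening), which describe people who could benefit from PrEP but are not on it.

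Table 28, which selects that cohort for Analysis #1, requires "No PrEP use between 21DEC2021 and 30JUN2023". Table 1 in Section 7.1 ends its follow-up at the first of "Death, loss to follow-up, study end (30JUN2024), 12 months after index date, PrEP initiation".

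The testing patterns that a reader would hold these rows against are given as intervals. Section 7.3.2 sets the oral PrEP testing schedule at "3 months (76-104 days) after each test". Section 5 states: "When CAB LA PrEP is used, HIV testing is recommended every 2 months, at the time the injection is administered". No footnote to the four tables, and nothing in Sections 7.3.2 or 7.7.1, redefines the quantity.

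**The concern.** A longer interval means less frequent testing. A larger number of events per week means more frequent testing. The label and the formula therefore point in opposite directions and carry different units. A reader who trusts the label will conclude that the group tested more often has the longer gaps, and cannot set the value against a schedule stated in days or months.

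In Tables 33 and 38 there is a second problem. The divisor is time on a PrEP type, in a cohort selected for not using PrEP and censored when PrEP starts.

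These are the only rows that summarise each person's testing or screening interval. Annex 1 says that the Analysis #2 tables will be identical apart from the study periods, so the error would be repeated.

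**Working it through.** The rows are unfilled shells, so the plan has no figure to reproduce. The check is one of dimension and direction. The test counts and the 52 weeks are assumptions for illustration: 4 tests is about one every 3 months, and 6 tests about one every 2 months.

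**Formulas.** As printed: value = events / weeks. An interval: value = weeks / events.

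| Tests in 52 weeks | As printed (events/week) | Interval (weeks) |
|---|---|---|
| 1 | 1/52 = 0.019 | 52/1 = 52.0 |
| 2 | 2/52 = 0.038 | 52/2 = 26.0 |
| 4 | 4/52 = 0.077 | 52/4 = 13.0 |
| 6 | 6/52 = 0.115 | 52/6 = 8.7 |
| 12 | 12/52 = 0.231 | 52/12 = 4.3 |

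**Direction.** From 4 to 6 tests the printed value is multiplied by 6/4 = 1.50, while the interval is multiplied by 4/6 = 0.67. If oral users tested about every 3 months and CAB LA users about every 2 months, the row would show 0.077 for oral and 0.115 for CAB LA. Under the label, CAB LA would seem to have an interval 50% longer, when it is 33% shorter.

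**Comparability.** The 76-104 day window in Tables 14 and 20 is 76/7 = 10.9 to 104/7 = 14.9 weeks. On the printed scale it becomes 7/104 = 0.067 to 7/76 = 0.092 per week. The interval of 13.0 weeks for 4 tests can be checked against the window directly; 0.077 cannot without inverting it. Table 33 uses a different window, 76-196 days, which is 10.9 to 196/7 = 28.0 weeks. The same mismatch applies there.

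**Denominator in Tables 33 and 38.** Under Table 28 there is no PrEP use in the inclusion period. Under Table 1 of Section 7.1, follow-up stops at PrEP initiation. Weeks on PrEP within follow-up are then 0, and events/0 is undefined for any number of events. Two features of the text could yield a positive number of weeks:

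- The Objective 6 censoring list for HIV diagnoses in Section 7.3.2 omits PrEP initiation, so on that list some people could accrue PrEP weeks after the inclusion period.
- People who qualify through a history of PrEP use have earlier PrEP weeks, but these lie outside follow-up.

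Neither gives a denominator that matches the period in which the tests are counted.

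**The case against.** The best defence is that the formula is printed in the row itself. As a rate it orders people correctly, and a median near 0.08 would hardly be taken for weeks between tests. That stands, and it rules out saying that the calculation itself ranks people the wrong way round. Only the reading under the label is reversed. The label is still what a reader takes from a published table, and it contradicts the definition beside it.

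The second defence is that no outcome depends on the row. This also stands. An average interval is not among the outcomes in Section 7.3.2. Frequency is reported as events per person and as rates per 100 person-years (Tables 13, 19, 34 and 39), and HIV schedule adherence has its own row directly below.

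The third is that the denominator in Tables 33 and 38 is wording carried over from the PrEP-user shells. That is probably so: other rows of those tables refer to the start of a PrEP type, and Tables 35 and 43 keep PrEP column headings. Section 7.7.1.1 does set the period, as the first visit with an indication and the following 12 months. This explains the error and points to the repair, but does not make the row computable as written.

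A reader might infer three further things that the documents do not support:

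- **Untested people enter the row as 0, the shortest interval.** The row follows a line counting people with any test and may be restricted to them. The protocol does not say.
- **The row fails Objective 6 because it cannot be set against the 2- or 3-month PrEP testing pattern.** Objective 6 sets no such pattern; Table 33 uses 3 to 6 months. For CAB LA users, on-schedule testing is itself defined around injection dates.
- **The zero denominator affects all four tables.** In Tables 14 and 20 the weeks are positive.

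**Conclusion.** The point holds as an error in four descriptive rows. In Tables 14, 20, 33 and 38 the definition is the reciprocal of the quantity named. In Tables 14 and 20 this reverses the oral versus CAB LA comparison for anyone reading the label, by a factor of 1.50 instead of 0.67 in the 4-versus-6-test illustration. In Tables 33 and 38 the row also lacks a usable denominator. That rests on the Table 28 selection and the censoring in Table 1 of Section 7.1; the shorter censoring list in Section 7.3.2 makes it zero for most rather than necessarily all, and does not rescue the row.

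The incidence estimates, the Poisson rates and the on-schedule percentages are untouched. The correction is worth making because the reported values would be wrong for their label in both analyses, and it costs little.

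**What to change.** Choose one definition and use it in all four tables.

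- **Rate form.** Rename the row as testing (or screening) events per week and keep people with no events as 0. This leaves the arithmetic in Tables 14 and 20 as it is.
- **Interval form.** Define the row as weeks of follow-up on the PrEP type divided by the number of events, among people with at least one event, and report the number with no event alongside. If days between consecutive events are used instead, restrict the row to people with at least two events, since one event gives no gap.

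In Tables 33 and 38, replace weeks on the PrEP type with weeks of follow-up from the index visit to censoring, and re-anchor the other rows that refer to the start of a PrEP type to the index visit.

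The cost is four row edits and one derivation, plus the re-anchored rows in Tables 33 and 38. The interval form has a price: people with no event, or only one, move to a separate row, and the summary then describes testers only. Weeks divided by events also gives a person with one test in 4 weeks an apparent 4-week interval, although no gap was observed. The rate form avoids both.

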7.5. Study size

Between 21DEC2021 and 30JUN2023 (Analysis #1 inclusion period), 22,234 adults without HIV started a new PrEP formulation in OPERA. The first formulation used during the study period was TAF/FTC oral (n=12,110, 54%), TDF/FTC oral (n=9,740, 44%), or CAB LA (n=384, 2%). An additional 292 individuals switched to CAB LA PrEP later during the study period, for a total of 767 people receiving CAB LA injections during the Analysis #1 inclusion period. Table 2 presents the precision estimates for proportions using a 95% confidence level, calculated using the standard confidence intervals equation $[p \pm 1.96\sqrt{(p*(1-p)/N)}]$. In both oral PrEP groups, the confidence interval width ranges from 0.01 to 0.02 for all proportions evaluated. For the CAB LA PrEP group, the confidence interval width ranges from 0.04 to 0.07 for all proportions evaluated.

Table 3. Precision estimates based on sample size and event proportions, using a 95% confidence level

PrEP formulation	Sample Size	Event Proportion	Lower Limit	Upper Limit	CI Width
CAB LA	767	0.1	0.08	0.12	0.04
	767	0.2	0.17	0.23	0.06
	767	0.3	0.27	0.33	0.06
	767	0.4	0.37	0.43	0.07
	767	0.5	0.46	0.54	0.07
	767	0.6	0.57	0.63	0.07
	767	0.7	0.67	0.73	0.06
	767	0.8	0.77	0.83	0.06
	767	0.9	0.88	0.92	0.04
TDF/FTC	9740	0.1	0.09	0.11	0.01
	9740	0.2	0.19	0.21	0.02
	9740	0.3	0.29	0.31	0.02
	9740	0.4	0.39	0.41	0.02
	9740	0.5	0.49	0.51	0.02
	9740	0.6	0.59	0.61	0.02
	9740	0.7	0.69	0.71	0.02
	9740	0.8	0.79	0.81	0.02
	9740	0.9	0.89	0.91	0.01
TAF/FTC	12110	0.1	0.09	0.11	0.01
	12110	0.2	0.19	0.21	0.01
	12110	0.3	0.29	0.31	0.02
	12110	0.4	0.39	0.41	0.02
	12110	0.5	0.49	0.51	0.02
	12110	0.6	0.59	0.61	0.02
	12110	0.7	0.69	0.71	0.02
	12110	0.8	0.79	0.81	0.01
	12110	0.9	0.89	0.91	0.01

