^a Assessed at the test-level

^b Multiple HIV tests on the same day count as one testing event

Table 17. Frequency and type of HIV tests among oral PrEP users, by healthcare clinic type^a

	Healthcare center	Wellness center	Other
Total number of HIV testing events ^b ordered			
Test type			
RNA only, n (%)			
Quantitative RNA test, n (%)			
Qualitative RNA test, n (%)			
Ag/Ab only, n (%)			
Rapid test only, n (%)			
Both RNA and Ag/Ab, n (%)			
Quantitative RNA test, n (%)			
Qualitative RNA test, n (%)			
Both RNA and rapid test, n (%)			
RNA, Ab/Ag and rapid tests, n (%)			
Testing on schedule (≤14 days before/at first injection or ±14 days of each subsequent injection, as applicable), n (%)			

^a Assessed at the test-level

^b Multiple HIV tests on the same day count as one testing event

Table 18. Frequency and type of HIV tests among CAB LA PrEP users, by healthcare clinic type^a

	Healthcare center	Wellness center	Other
Total number of HIV testing events ^b ordered			
Test type			
RNA only, n (%)			
Quantitative RNA test, n (%)			
Qualitative RNA test, n (%)			
Ag/Ab only, n (%)			
Rapid test only, n (%)			
Both RNA and Ag/Ab, n (%)			
Quantitative RNA test, n (%)			
Qualitative RNA test, n (%)			
Both RNA and rapid test, n (%)			
RNA, Ab/Ag and rapid tests, n (%)			
Testing on schedule (≤14 days before/at first injection or ±14 days of each subsequent injection, as applicable), n (%)			

^a Assessed at the test-level

^b Multiple HIV tests on the same day count as one testing event

Table 19. Incidence rate of STI screening events within 12 months of index among PrEP users^a

	Oral PrEP N=	CAB LA PrEP N=
Total # STI screening events within 12 months of index, n		
Person-years of follow-up		
IR per 100 py (95% CI)		

Table 20. Frequency and type of STI screening among PrEP users^a

	Oral PrEP N=	CAB LA PrEP N=
STI screening within 14 days before/on day of PrEP type start, n (%)		
STI tested, n (%)		
Syphilis		
Gonorrhea		
Chlamydia		
Chancroid		
Lymphogranuloma venereum		
Mycoplasma genitalium		
Herpes Simplex-2		
Trichomoniasis		
Human papilloma virus/genital warts		
HBV		
HCV		
Days from test to PrEP type start, median (IQR)		
Any STI screening within 12 months after PrEP type start, n (%)		
Number of STI screening events ^b , median (IQR)		
Syphilis, n (%)		
Gonorrhea, n (%)		
Chlamydia, n (%)		
Chancroid, n (%)		
Lymphogranuloma venereum, n (%)		
Mycoplasma genitalium, n (%)		
Herpes Simplex-2, n (%)		
Trichomoniasis, n (%)		

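### The on-schedule row of Annex Table 17 (oral PrEP users, by clinic type) carries the CAB LA injection rule and contradicts the oral definition in section 7.3.2 and Table 15

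*Protocol*

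**What the plan says.** Section 7.3.2 gives two separate definitions of on-schedule HIV testing. For oral users: "Oral PrEP: on-schedule testing defined as receiving an HIV test ≤14 days before/at start, and 3 months (76-104 days) after each test". For injection users: "LA PrEP: on-schedule testing defined as receiving an HIV test ≤14 days before/at first injection, and ±14 days of each subsequent injection". The first is anchored to PrEP start and the previous test, the second to injection dates.

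The Annex 1 shells apply these as follows:

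- Table 14 (both PrEP types) keeps the two rules apart: "Testing on schedule (oral: every 3 months (76-104 days); CAB LA: ±14 days of each injection), n". Table 25 uses the same split.
- Table 15 (oral, by provider type) uses the oral rule: "Testing on schedule (≤14 days before/at start or 3 months (76-104 days) after the last test, as applicable), n".
- Tables 16 and 18 (CAB LA, by provider type and by clinic type) use the injection rule.
- The remaining shell is titled "Table 17. Frequency and type of HIV tests among oral PrEP users, by healthcare clinic type", and its row is "Testing on schedule (≤14 days before/at first injection or ±14 days of each subsequent injection, as applicable), n".

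The footnotes to Table 17 cover only test-level assessment and the counting of same-day tests. Neither changes the rule. The opening of Annex 1 says that the Analysis #2 tables will be the same apart from the study periods.

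**The concern.** Table 17 is the only shell that reports oral on-schedule testing by clinic type. Its row measures the distance from a test to an injection in people who, while on oral PrEP, are not receiving injections. A programmer who follows the shell would produce a figure that says nothing about oral testing practice and could be read as almost complete failure to test on time at every clinic type. A programmer who notices and silently substitutes the oral rule would depart from the protocol without a record. Because the shells carry over to Analysis #2, either outcome would occur twice.

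**Working it through.** The plan states no figure for this row, so there is nothing to reproduce. The check compares the texts and then sizes the effect with the counts in section 7.5.

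**1. Text comparison.** Tables 14, 15 and 25 use the 76 to 104 day interval for oral users, as section 7.3.2 does. Table 17 is the only oral on-schedule row that does not, and its wording is identical to that of Tables 16 and 18. This looks like a row copied from a CAB LA shell.

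**2. One record under both rules (illustration).** Take an oral user with no injections, tested on days 0, 90, 180 and 270.

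- Oral rule: day 0 is at start, so it counts. The later gaps are 90 − 0 = 90, 180 − 90 = 90 and 270 − 180 = 90 days, all within 76 to 104. Result: 4 of 4.
- Table 17 rule: there is no injection date, so no test can match. Result: 0 of 4, or undefined if the words on applicability are read as removing these tests from the denominator.

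**3. How many oral users have an injection date.** Inputs from section 7.5 (Analysis #1 inclusion period): TAF/FTC 12,110, TDF/FTC 9,740, CAB LA 384 at index, 292 later switchers to CAB LA, and 767 CAB LA recipients in total.

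- Index oral users: 12,110 + 9,740 = 21,850.
- Share of all index users: 21,850 / 22,234 = 98.3%.
- Later switchers: 292 as stated, or 767 − 384 = 383 from the stated total. The two do not agree (384 + 292 = 676, not 767), so both are carried as a range.
- Share of index oral users with an injection date: 292 / 21,850 = 1.3% to 383 / 21,850 = 1.8%.
- Share without: 98.7% to 98.2%, so about 98%.

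**4. What the row could show.** Assume that each switcher to CAB LA contributes one oral-period test in the 14 days up to the first injection, and that everyone has k tests. The on-schedule percentage is then switchers / (21,850 × k).

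- 292 switchers, k = 5: 292 / 109,250 = 0.3%.
- 383 switchers, k = 1: 383 / 21,850 = 1.8%.

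People who start on CAB LA and move to oral can add to this if an oral-period test falls within 14 days of a second or later injection. As a generous case, let all 384 index CAB LA users do so with one qualifying test each: (383 + 384) / (21,850 + 384) = 767 / 22,234 = 3.4% at k = 1, and 767 / (22,234 × 5) = 0.7% at k = 5.

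**5. Agreement with Table 15.** Tables 15 and 17 are both assessed at test level and divide oral users' test events, once by provider and once by clinic. Summed over columns, their on-schedule counts should agree, apart from events that cannot be assigned to a clinic type. With different rules in the two rows they cannot.

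**The case against.** The strongest reply is that the governing definition is correct and clear. Section 7.3.2 states the oral rule separately, three other shells apply it, and Table 17 is a single outlier. A sensible programmer would see that injection timing has no meaning for people without injections, and a near-zero row beside Table 15 would be conspicuous. This stands, and it limits the severity. It does not remove the contradiction. Section 7.8 does include a check of reports against their specification, but if the shell is taken as the specification, that check could confirm the wrong row.

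Three stronger readings are tempting, and the documents do not support them.

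- A reader might infer that the oral result by clinic type cannot be produced. It can, by applying the oral definition in section 7.3.2. No definition is missing.
- A reader might infer that Objective 5 loses its clinic-type result for oral users. Section 7.3.2 describes that result as "HIV testing practices (type, frequency) by clinic type (healthcare center, wellness center, other", and section 7.7.1.1 likewise names frequency and type. Schedule adherence by clinic type appears only in the shells. The rows for number and type of tests are unaffected, as is the overall oral figure in Table 14.
- A reader might infer that the printed row must be exactly 0%, or that only later switchers to CAB LA could meet it. Table 5 also provides for switches from CAB LA to oral, and the footnote to Table 11 counts those people's oral follow-up. Switchers in either direction could produce a small non-zero figure.

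**Conclusion.** The row is wrong as written, and the point is minor. Table 17 contradicts section 7.3.2 and Table 15. Followed literally, its on-schedule figure by clinic type would be near zero or undefined: about 0.3% to 1.8% under the switcher assumptions above, and 3.4% in the generous two-way case.

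This sizing rests on assumed numbers of tests per person and on one qualifying test per switcher. It also uses switch counts for the Analysis #1 inclusion period only, so switches later in follow-up would raise the percentages somewhat. The contradiction does not depend on any of these assumptions. The study population, the HIV incidence results and the coverage results are not touched.

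**What to change.** Replace the Table 17 row with the row already used in Table 15, "Testing on schedule (≤14 days before/at start or 3 months (76-104 days) after the last test, as applicable), n", so that it matches section 7.3.2, and carry the correction into the Analysis #2 shells. The cost is one shell row: no new data, no added analysis, and no change to any clinical recommendation, since the wording is the protocol's own measurement definition.
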